8 STUDY ASSESSMENTS AND PROCEDURES

8.1 EFFICACY ASSESSMENTS

a. Admission/Enrollment Procedure

All women in the 4 study health centers are educated about postpartum contraception during antenatal care. All postpartum women who do not receive an IPP IUD or tubal ligation will be asked if they are interested in the IUD for contraception while on the postpartum floor. If they plan to choose an IUD they will be asked for verbal assent to be pre-screened for the study. If a woman gives verbal consent to be pre-screened, a research assistant will administer the Pre-Participation Questionnaire/Eligibility Checklist. Women who meet inclusion criteria, meet no exclusionary criteria, and want to participate, will be formally consented to participate in the study. Signed informed consent forms will be collected. Subjects will be given copies of the consent document and a copy of the "Experimental Subject's Bill of Rights," and a HIPAA Authorization form for medical data to be released for research purposes. Enrolled participants will then be randomized to EPP or Interval PP IUD placement within 10 days of delivery. The Research Assistant (RA) will open the sealed envelope with the appropriate randomization envelope for the assigned participant number to unblind the participant to her assigned group. Participant numbers are assigned sequentially by each site. Participants will then be asked to complete the Baseline questionnaire.

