For women who believe they want an IUD postpartum but are unsure whether or not they would like to be part of the study, study staff will provide them with our contact information, an informed consent form, a Subject's Bill of Rights, and a HIPAA Authorization form for medical data to be released for research purposes. If they decide they are interested in participating while they are still in the hospital, the RA will go to their postpartum floor within 24 hours and will pre-screen/enroll as outlined above. For interested women who are being discharged from the hospital, staff will ask them to call us to discuss the study. Over the phone, the RA will ask for verbal consent to pre-screen for the study. If a woman gives verbal consent to be pre-screened, the RA will administer the Pre-Participation Questionnaire/Eligibility Checklist. For women who meet inclusion criteria, meet no exclusionary criteria, and want to participate, the RA will review the Informed Consent and HIPAA Authorization forms and then ask the woman to sign the forms and bring the signed copies to their first study visit. The woman will be officially enrolled in the study at that point. The RA will then open the randomization envelope and schedule the first study visit at either 2 weeks or 6 weeks postpartum once the consent is

signed. The RA will administer the Enrollment Survey either over the phone or in person before the first research visit.

b. Two Week Postpartum Visit

All women randomized to EPP will be scheduled to have an IUD placement visit with their designated prenatal care provider **between 14 and 28 days**. Women will be scheduled to see a nurse midwife or physician based on their obstetrical history and prenatal care. IUDs will be placed by the patient's usual prenatal provider or any provider that the patient would normally be referred to for IUD placement. Whether ultrasound guidance is used for placement will be at the discretion of the clinician. Participants will be compensated with a \$20 gift card for their time and participation after completing the IUD Insertion survey. If a patient in the interval group is seen by her provider at 2 weeks postpartum for other reasons an IUD will not be placed at that visit. Providers will be compensated with a \$5 gift card for their time completing a brief questionnaire for every patient seen at 2 weeks who is participating in the study.

c. Six Week Postpartum Visit

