All women will be scheduled to have a routine postpartum visit with their designated prenatal care provider **between 42-56 days postpartum** according to the standard of care at the health centers. Women will be scheduled to see a nurse midwife or physician based on their obstetrical history and prenatal care. Women in the interval group will be assessed for IUD placement at this visit per the standard of care at the center. IUDs will be placed by the patient's usual prenatal provider or any provider that the patient would normally be referred to for IUD placement. Whether ultrasound guidance is used for placement will be at the discretion of the clinician. Participants will be compensated with a \$20 gift card for their time and participation. Participants will be asked to complete either the insertion visit questionnaire or the string check questionnaire depending on their assignment group. Providers will be compensated with a \$5 gift card for their time completing a brief questionnaire for every patient seen at six weeks postpartum.

D. Optional String Check Visit:

Whether a follow-up string check visit is scheduled after six weeks will be at the discretion of the clinician according to standard practice of the clinic. String checks are not recommended by the CDC but are common practice. If a string check is scheduled by the clinician at any time (according to their personal practice or participant needs) then the participant will be asked to complete the string check questionnaire at that time.

e. Six Month Follow Up Visit

All women will be scheduled for a 6-month follow up study visit to assess for IUD expulsion, perforation, pregnancy, IUD removals and acceptability. A study clinician will conduct a bimanual pelvic exam, a speculum exam, and a transvaginal ultrasound at this visit. Women will also be asked to complete the 6-month study questionnaire and will be compensated with a \$20 gift card for their time and participation. The clinician will attempt to stay blinded to the participant's group assignment by not reviewing the medical chart prior to the visit.

f. 12 Month Optional Follow Up Call

During baseline survey data collection, all women will be asked if they consent to a 12-month follow up phone call to assess for IUD expulsion, perforation, pregnancy, IUD removals and acceptability.

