9.4.5 BASELINE DESCRIPTIVE STATISTICS

Baseline characteristics such as demographic information (age, education level, race, ethnicity and employment status) will be collected. At the time of enrollment, questions will also be asked about pregnancy history, past use of contraception, breastfeeding status and future fertility desires. Means and proportions of respondents in each of the two groups will be compared to assess for success of randomization.

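### Baseline questionnaire and 12-month-call consent are collected after the allocation is revealed, so a few baseline items, survey completion and the 12-month subset can differ by arm because of the allocation

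*Combined protocol and SAP*

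**What the plan says.** Section 8.1a of the combined protocol and SAP describes two enrollment routes.

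- **In hospital.** After pre-screening and consent, "Enrolled participants will then be randomized to EPP or Interval PP IUD placement within 10 days of delivery". The research assistant opens the envelope "to unblind the participant to her assigned group". The next step is "Participants will then be asked to complete the Baseline questionnaire".
- **By phone after discharge.** Once consent is signed, "The RA will then open the randomization envelope and schedule the first study visit at either 2 weeks or 6 weeks postpartum". The sentence that follows is "The RA will administer the Enrollment Survey either over the phone or in person before the first research visit".

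The first visit depends on the arm. In 8.1b the early arm is seen "between 14 and 28 days" after delivery. In 8.1c the interval arm is seen on days 42 to 56.

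Section 8.1f adds: "During baseline survey data collection, all women will be asked if they consent to a 12-month follow up phone call".

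Section 9.4.5 includes breastfeeding status and future fertility desires among the baseline questions, says they are asked at enrollment, and gives their use: "Means and proportions of respondents in each of the two groups will be compared to assess for success of randomization". Section 6.2 states that participants are not blinded. No section requires the questionnaire or the 12-month consent to be completed before the envelope is opened.

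**The concern.** A between-arm comparison of baseline data can speak to the randomization only if the data could not have been affected by the allocation. Here the woman knows her arm when she answers, and in the phone route the time allowed for answering depends on her arm. Some answers can change over the weeks after delivery or be given in light of the assignment, and a woman may be more or less willing to complete the form once she knows her arm.

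Two uses of the data are at stake. First, a difference seen in 9.4.5 could come from the allocation and not from chance, or a chance imbalance could be hidden. Second, women who agree to the 12-month call could be selected differently in the two arms, because they decide after learning their assignment.

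**Working it through.** The plan states no figure on this point to reproduce. The check has three steps: the order of events, day arithmetic for the phone route, and a sort of the items by susceptibility.

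**1. Order of events**

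- In hospital: consent, randomization, envelope opened and arm disclosed, questionnaire. The order is explicit.
- Phone: signed consent, envelope, first visit scheduled by arm, survey. The survey follows the envelope in the text, and its only stated limit in 8.1 is the first visit.
- Section 9.4.5 places the questions at enrollment. That is tighter than the limit in 8.1a, so the two must be reconciled. It does not say that the questions come before the envelope, so it narrows the possible delay without restoring the order.

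**2. Time allowed in the phone route**

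Inputs: randomization on day 0 to 10 (8.1a); first visit on day 14 to 28 in the early arm (8.1b) and day 42 to 56 in the interval arm (8.1c).

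Shortest gap from randomization to first visit = first day of visit window − 10:
- early arm: 14 − 10 = 4 days
- interval arm: 42 − 10 = 32 days

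Longest gap = last day of visit window − 0:
- early arm: 28 − 0 = 28 days
- interval arm: 56 − 0 = 56 days

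Difference between the arms in the outer limit for the survey: 56 − 28 = 28 days at the end of the windows, and 42 − 14 = 28 days at the start. So 8.1a, read alone, lets the survey be taken up to 28 days later in the interval arm.

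**3. What can be affected**

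- Facts such as age, race, ethnicity, pregnancy history and past contraceptive use: the content would not plausibly change with the allocation. Whether the form is completed can.
- Breastfeeding status and future fertility desires: the content can change with time or with knowledge of the arm.
- Consent to the 12-month call: can depend on knowledge of the arm.

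**4. Where the data are used**

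Section 9.4.2 compares complete expulsion between arms by an unadjusted Wald test. Section 9.4.3 uses the same methods for partial expulsion and perforation, an unadjusted log-rank test for discontinuation, and two-group tests for the rest. None uses a baseline covariate. The baseline data enter the comparison in 9.4.5. The 12-month consent determines who is called, and no 12-month analysis is specified.

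**The case against.** The strongest reply is that no planned inference depends on these data. The primary and secondary analyses are unadjusted. Section 9.4.5 has no named test, threshold or resulting action. The 12-month call is optional, and the stated objectives and hypotheses concern 6 months. Most baseline items are fixed facts. An intention to conceive within 6 months is already an exclusion (5.2), checked before allocation, and randomization is stratified by IUD type and site (6.2). All of this stands, and it limits the point to the randomization check and the 12-month subset. It does not reverse the order in 8.1a.

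A second reply is that the first-visit limit is only an outer deadline, because 9.4.5 places the questions at enrollment and 8.1a calls the phone instrument an Enrollment Survey. This stands in part: a survey near day 56 is permitted by 8.1a but need not be intended. That the Enrollment Survey is the Baseline questionnaire is a reasonable reading, not a stated one.

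A reader might go further in three ways that the documents do not support.

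- **A count of women affected.** An assumed phone share of 10% to 30% would give 404 × 0.10 = 40 to 404 × 0.30 = 121 women. The share is not in the documents, and the count covers both arms. Only interval-arm women could be surveyed after day 28: 202 × 0.10 = 20 to 202 × 0.30 = 61 under the same assumption, and only if staff waited that long.
- **Loss of breastfeeding as a covariate for perforation.** Section 2.2 links the two, but no adjusted model is planned and perforation is exploratory (section 3). Section 9.4.2 says imputation will be considered but names no predictors.
- **Disappointment over a preferred timing.** The documents do not describe asking women which timing they prefer.

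A third reply concerns the remedy: a phone enrollee should not give research data before her consent is signed. This stands, and the fix below provides for it.

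**Conclusion.** The point holds in a limited form. For in-hospital enrollees it is explicit that the questionnaire follows disclosure of the arm. For phone enrollees the survey follows the envelope in the text, and the only limit in 8.1a depends on the arm and does not match 9.4.5. Breastfeeding status, future fertility desires, survey non-response and 12-month consent can therefore differ because of the allocation. The check in 9.4.5 is weakened for those items and for completeness, and the optional 12-month subset may not be comparable between arms.

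The 28 days is the difference between the permitted limits, not an expected difference in survey dates. The number of women cannot be computed without the phone-enrolled share. The phone-route finding assumes that the two survey names mean one instrument.

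A reader might infer that the non-inferiority result is biased or that the randomization itself is compromised. Neither follows. The 6-month comparisons use none of these data, and the order of the questionnaire does not change how women are allocated. The documents permit arm-dependent baseline data; they do not show that any imbalance occurred.

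**What to change.** In 8.1a, set one order for both routes: signed consent, then the Baseline questionnaire including the request for the 12-month call, then the envelope, all within the 10-day randomization window. In the phone route, replace the first-visit limit with: after consent is signed and before the envelope is opened. Use one name for the instrument, and align the timing in 8.1a, 8.1f and 9.4.5.

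For phone enrollees, also state how the site confirms that consent is signed before it asks the questions. Section 8.1a has these women bring the signed forms to the first visit, yet opens the envelope, which determines that visit, only once consent is signed.

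The cost is a slightly longer enrollment contact. The instrument, staff, sample size and planned analyses stay as they are. If women have already been enrolled under the current order, report survey dates relative to allocation by arm, and label the susceptible items as collected after allocation.

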8.3.4 TIME PERIOD AND FREQUENCY FOR EVENT ASSESSMENT AND FOLLOW-UP

The occurrence of an adverse event (AE) or serious adverse event (SAE) may come to the attention of study personnel during study visits and interviews of a study participant presenting for medical care, by communication from the participant to the study team, or upon review by a study monitor.

All AEs including local and systemic reactions not meeting the criteria for SAEs will be captured. Information to be collected includes event description, time of onset, clinician's assessment of severity, relationship to study product (assessed only by those with the training and authority to make a diagnosis), and time of resolution/stabilization of the event. All AEs occurring while on study must be documented appropriately regardless of relationship. All AEs will be followed to adequate resolution.

Any medical condition that is present at the time that the participant is screened will be considered as baseline and not reported as an AE. However, if the study participant's condition deteriorates at any time during the study, it will be recorded as an AE. Changes in the severity of an AE will be documented to allow an assessment of the duration of the event at each level of severity to be performed. AEs characterized as intermittent require documentation of onset and duration of each episode.

At each study visit, the investigator will inquire about the occurrence of AE/SAEs since the last visit. Events will be followed for outcome information until resolution or stabilization.

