9 STATISTICAL CONSIDERATIONS

9.1 STATISTICAL HYPOTHESES

- Primary Efficacy Endpoint: Complete expulsion of IUDs placed in the early postpartum is non-inferior to IUDs placed at the standard interval time, assuming a 6% non-inferiority margin.
- Secondary Efficacy Endpoints:
 - The proportion of participants utilizing the IUD at 6 months postpartum will be greater in the EPP group compared to the interval group.
 - Partial expulsion of IUDs placed in the early postpartum is non-inferior to IUDs placed at the standard interval time, assuming a 6% non-inferiority margin.
 - There will not be a clinically or statistically significant difference in the proportion of participants diagnosed with a pelvic infection.
 - Proportion of participants agreeing or strongly agreeing that they are satisfied with the IUD, and the timing of IUD placement, will be similar between groups.

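### The early arm has a scheduled contact 14-42 days after insertion and the interval arm none until about 124-141 days, so pelvic infection, pain and bleeding may be captured less fully in the interval arm

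*Combined protocol and SAP*

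**What the plan says.** Section 8.1 sets the visits by days since delivery.

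- **Early insertion (item b):** "All women randomized to EPP will be scheduled to have an IUD placement visit with their designated prenatal care provider between 14 and 28 days".
- **Six-week visit, both arms (item c):** "All women will be scheduled to have a routine postpartum visit with their designated prenatal care provider between 42-56 days postpartum". For the control arm this is the insertion visit: "Women in the interval group will be assessed for IUD placement at this visit per the standard of care at the center". The form differs by arm: "Participants will be asked to complete either the insertion visit questionnaire or the string check questionnaire depending on their assignment group".
- **Later string check (item D):** "Whether a follow-up string check visit is scheduled after six weeks will be at the discretion of the clinician". The string check questionnaire is completed if such a visit is scheduled.
- **Six-month visit (item e):** every woman has the same pelvic, speculum and ultrasound examination and the same questionnaire.

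On adverse events, section 8.3.4 states: "At each study visit, the investigator will inquire about the occurrence of AE/SAEs since the last visit". It also allows events to come to light through medical care, participant communication or monitoring. Section 9.4.4 has events recorded when the team learns of them.

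The synopsis lists pelvic infection, pain and vaginal bleeding among the secondary outcomes at 6 months postpartum. Section 9.1 adds a hypothesis on infection: "There will not be a clinically or statistically significant difference in the proportion of participants diagnosed with a pelvic infection". Section 9.4.3 compares proportions with chi-square or Fisher's exact tests and makes no allowance for time since insertion or for the source of the report.

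**The concern.** The six-week visit plays a different part in each arm. In the early arm it is a post-insertion follow-up with a questionnaire about the device. In the interval arm it is the insertion itself, so nothing about that insertion can yet be reported. After it, no contact is required in the interval arm for roughly four months.

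If events are asked about soon after insertion in one arm and only months later in the other, minor or resolved infections, pain and bleeding may be reported more completely in the first. A between-arm difference could then come from the visit schedule and not from the timing of insertion. A true advantage of early insertion could equally be cancelled out. The infection hypothesis is the most exposed, because it predicts no difference and the analysis has no means of separating the two explanations.

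**Working it through.** The plan gives no figure for time since insertion, so there is none to reproduce. The lags follow from its own visit windows.

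**Inputs**
- Early insertion: day 14-28 (section 8.1, item b).
- Six-week visit, and interval insertion: day 42-56 (section 8.1, item c).
- Six-month visit: no window is given. Assumed day 180-183.
- Latest accepted outcome: day 240 (section 9.3, footnote).
- Women per arm: 202 (section 9.2).

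**Step 1. Lag to the first scheduled post-insertion contact** (visit day minus insertion day)

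| Arm | Shortest | Longest | Weeks |
|---|---|---|---|
| Early (six-week visit) | 42 - 28 = 14 days | 56 - 14 = 42 days | 2.0-6.0 |
| Interval (6-month visit) | 180 - 56 = 124 days | 183 - 42 = 141 days | 17.7-20.1 |

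If the interval-arm outcome is obtained at the day 240 limit, the lag is 240 - 56 = 184 to 240 - 42 = 198 days.

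**Step 2. Scheduled post-insertion contacts through 6 months.** Early arm: six weeks and 6 months, so two. Interval arm: 6 months only, so one.

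**Step 3. Time since insertion at the 6-month visit.** Taking day 182 and window midpoints (day 21 and day 49): early 182 - 21 = 161 days, interval 182 - 49 = 133 days. The early arm has 28 days more in which an event can occur, a ratio of 161/133 = 1.21.

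**Step 4. Possible size of the artefact (illustration; both inputs are assumed).** Let p be a true event risk that is equal in both arms, and s the share of events that late-only inquiry captures relative to inquiry that includes the early contact. The spurious early-arm excess is p x (1 - s).

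| p | s = 0.9 | s = 0.7 | s = 0.5 |
|---|---|---|---|
| 2% | 0.2 points | 0.6 points | 1.0 points |
| 5% | 0.5 points | 1.5 points | 2.5 points |
| 10% | 1.0 points | 3.0 points | 5.0 points |

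With 202 women per arm, the extremes are 0.002 x 202 = 0.4 and 0.050 x 202 = 10.1 women. The documents give neither p nor s, so the table shows scale and is not an estimate.

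**The case against.** A reader might infer that expulsion, including the primary endpoint, is also ascertained unequally. The documents do not support that. Section 3 defines complete and partial expulsion by speculum and ultrasound examination at 6 months. Section 8.1 gives every woman that examination, by a clinician who tries to remain blinded. The early arm does have an additional earlier chance of detection and about 28 more days at risk. Both would add expulsions to the early arm and so count against non-inferiority.

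A reader might also infer that adverse events are captured only at visits, or that nothing reaches interval-arm women before 6 months. That goes too far. Section 8.3.4 names other routes, section 2.3.1 provides record access for clinical outcomes, and section 8.1 calls string checks common practice. The infection hypothesis concerns diagnosed infection, which should leave a record. Randomization is stratified by site, so differences in clinic practice are balanced between arms. All of this stands, and it makes the imbalance smaller. It does not remove it: string checks are discretionary, the other routes are passive, and the plan does not make the record the source for infection or set a window for it.

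Two further points stand. The questionnaires are not in the documents, so it cannot be confirmed that the string check form asks about infection, pain or bleeding. An adverse event inquiry at six weeks in the early arm depends on counting that routine visit as a study visit; the study questionnaire and payment given there support this reading, but no text states it. If these outcomes were taken from the 6-month questionnaire alone, the additional early contact would not enter the comparison. The plan does not say which source is used.

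Finally, the effect may be small. With a 2% risk, and 90% against 60% capture (all assumed), the arms would show 1.8% and 1.2%, or 3.6 and 2.4 women of 202.

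**Conclusion.** The point holds for solicited secondary and safety outcomes. By schedule, the first post-insertion contact falls at 14-42 days in the early arm and at about 124-141 days in the interval arm, with two contacts against one. Pelvic infection, pain and bleeding may therefore be captured more fully in the early arm.

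The direction matters. Fuller early-arm capture would overstate early-arm harm or mask an early-arm benefit; it would not hide an early-arm harm. The primary non-inferiority conclusion is not undermined.

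The lags rest on insertion within the planned windows and on a 6-month visit near day 180-183. The effect on results rests on the six-week contact eliciting these events and feeding the comparison, which the documents suggest but do not state. The range of 0.2 to 5.0 points is illustrative only. The correction is worth making because it is cheap and removes a schedule-driven bias from the infection comparison.

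**What to change.** **Preferred:** give the existing string check questionnaire and the adverse event inquiry by phone or text at the same time since insertion in both arms, for example 4 weeks after insertion. The cost is one short contact per woman by existing staff. Sites already use phone calls and texts, although the site that works on paper and fax would have one more form to send. No visit or examination is added.

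**Alternative with no added contact:** state in section 9.4.3 that diagnosed pelvic infection will also be compared from the medical record over an equal number of days since insertion in both arms, for example days 0-126, alongside the planned comparison at 6 months postpartum. The limit of 126 is the follow-up available to a woman with insertion on day 56 if 6 months is day 182 (182 - 56 = 126). The modified intention-to-treat set admits insertions up to 6 months after delivery, so the text should say how women with shorter follow-up are handled. The cost is SAP wording and record abstraction under access the protocol already has. This covers infection but not self-reported pain or bleeding.

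Under either option, the plan should name the source and time window for infection, pain and bleeding.
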